15.3. Financial conditions

[figure not shown]
Coloplast A/S will compensate all the investigators involved in the clinical investigation for their time and resources spent on the investigation. All financial agreements with the investigation sites involved in the clinical investigation will be specified in a sponsor investigator contract.

Investigator fee, excluding subject compensation, is estimated up to [REDACTED]. The investigator has no apparent conflict of interest.

16. Indemnity and Subject compensation

[figure not shown]
16.1. Indemnity

All subjects are fully covered by Coloplast A/S insurance throughout the investigation:

16.2. Compensation for participating in the clinical investigation

Subjects will be compensated with a voucher per visit to [REDACTED], paid by Coloplast A/S with the value as described below:

This is to compensate for any inconvenience caused during the catheterisations, time used. Travel expenses will be accounted for separately. The remuneration/vouchers are taxable (B-income) and it is the responsibility of the subject to declare this to SKAT.

17. Adverse events, adverse device effects and device deficiencies

17.1. Adverse events

An adverse event is any untoward medical occurrence, unintended disease or injury, or untoward clinical signs (including abnormal laboratory findings) in subjects, users or other parties, whether or not, related to the medical device(s), or the procedures involved. This could include events such as headache or dizziness.

17.2. Adverse device effect

An adverse event, which is related to the use of the investigational medical device, is an adverse device effect, and should be marked as related or possibly related on the adverse event form.

The definition of an adverse device effect includes any event resulting from insufficiencies or inadequacies in the instruction for use, or any malfunction of the medical device, as well as any event resulting from use error or from intentional misuse of the device. Table 2 lists anticipated adverse device effects that may occur.

Table 2: Anticipated adverse device effects and their likely incidence rates

ANTICIPATED ADES	LIKELYHOOD
Urinary tract infection	Very unlikely
Macroscopic haematuria	Unlikely
Macroscopic leukocytes	Unlikely
Stinging and pain in urethra during catheterisation	Likely
Irritation of mucosa	Likely

17.3. Device deficiency

A device deficiency is the inadequacy of the investigational medical device or comparator with respect to its identity, quality, durability, reliability, safety or performance. This includes malfunctions, use errors and inadequacy in the information supplied by the manufacturer including labelling.

17.4. Serious adverse events (SAE)

A serious adverse event is an adverse event that:

- Led to death,
- Led to a serious deterioration in the health of the subject, users or other persons as defined by one or more of the following:
 - 1) a life-threatening illness or injury, or
 - 2) a permanent impairment of a body structure or a body function including chronic diseases, or
 - 3) in-patient or prolonged hospitalization, or
 - 4) medical or surgical intervention to prevent life-threatening illness or injury or permanent impairment to a body structure or a body function.
- Led to fatal distress, fatal death or a congenital abnormality or birth defect.

This includes device deficiencies that might have led to a serious adverse event if:

- Suitable action had not been taken, or
- Intervention had not been made, or
- Circumstances had been less fortunate

These are handled under the serious adverse event reporting.

Planned hospitalization for a pre-existing condition, or a procedure required by the Clinical Investigation Plan, without serious deterioration in health, is not considered a serious adverse event.

17.4.1. **Serious adverse device effect (SADE)**

A serious adverse device effect is an adverse device effect that has resulted in any of the consequences characteristic of a serious adverse event.

17.4.2. **Anticipated serious adverse device effect (ASADE)**

There are no anticipated SADEs.

17.4.3. **Unanticipated serious adverse device effect (USADE)**

An unanticipated serious adverse device effect is a serious adverse device effect which by its nature, incidence, severity or outcome has not been identified in the current version of the risk analysis report.

17.5. **Medical care of subjects**

The principal investigator shall ensure that adequate medical care is provided to a subject experiencing an adverse event during and after participation in the clinical investigation. All serious adverse events will be followed until a resolution is addressed.

Subjects are informed to contact the investigator if any AEs should occur during the investigation. Furthermore, the investigator will inform the subjects to contact him should SAEs occur within one week of the subject is terminated from the investigation. Subjects are informed to contact their general physician in case of any AEs happening later than one week of investigation termination.

The status of all ongoing adverse events is documented during site close-out.

17.6. **Reporting and timelines**

17.6.1. **Investigator's reporting responsibilities**

- The principal investigator at each site must assess all (S)AE's that occur at his/her site.
- All serious adverse events and serious adverse device effects must be reported to sponsor within 24 hours of the site becoming aware of the event.
- A device deficiency that could have led to a serious adverse event but did not because suitable action was taken, intervention had been made or because of fortunate circumstances should be reported to sponsor within 24 hours of the site becoming aware of the event.
- New findings and/or updates in relation to already reported serious events should also be reported to sponsor within 24 hours of the site becoming aware of the event.
- Device deficiencies and all adverse device effects must be reported to sponsor within 10 days of becoming aware of the event.

When reporting the SAE, the relationship to the test material shall be described whether the event is considered

- **Not related**, the event has no temporal relationship with the use of the test material or the procedures.
- **Unlikely related**, the relationship with the use of the test material seems not relevant and/or the event can be reasonably explained by another cause, but additional information may be obtained.

- **Possibly related**, the relationship with the use of the test material is weak but cannot be ruled out completely. Alternative causes are also possible (e.g. an underlying or concurrent illness/ clinical condition or/and an effect of another device, drug or treatment). Cases where relatedness cannot be assessed or no information has been obtained should also be classified as possible.
- **Probably related**, the relationship with the use of the test material seems relevant and/or the event cannot reasonably be explained by another cause, but additional information may be obtained.
- **Definitely related/Causal relationship**, the event has a temporal relationship with the test material use/application or procedures.

All above events must be reported by use of the relevant adverse event/serious adverse event/device deficiency form.

Please report to [REDACTED] In cases where accessing e-mail is not possible, please call Clinical Manager, [REDACTED]

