6.3. Subject withdrawal criteria

The subject can withdraw from the investigation at any time for whatever reason without any consequences for their future treatment outside the clinical investigation. Investigator may withdraw a subject from the investigation at any time if they judge it to be the subject's interest.

The investigator must withdraw a subject from the investigation:

- If subject's safety and wellbeing is compromised by further participation.
- Due to non-compliance with the Clinical Investigation Plan impacting the scientific integrity of the investigation
- Pregnancy (see section 6.1.3 Pregnancy and breastfeeding)

Replacements can be made as a sponsor decision. Replacements will be allocated to the same sequence as the withdrawn subject.

If a subject terminates the investigation before investigation completion, the subject will be informed to contact the site within the first week after termination in case of questions or issues they want to discuss related to this investigation. If they have questions more than a week after termination, they are informed to contact their practitioner.

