9.3. Monitoring visits

The monitor is to ensure adherence to the clinical investigation plan, accurate data recording on the e-CRFs and to monitor recruitment rates and adherence to follow-up schedules. The investigator shall permit and assist the monitor to carry out verification of completed e-CRFs against data in the source documents.

The principal investigator can delegate tasks to his/her collaborators, however the roles and responsibilities as time of involvement for each clinical site personnel must be documented on the delegation log as well as training received before getting involved with the clinical investigation must be documented in the training log.

Before doing any review of subject data, the monitor must review the signed Informed Consent Form(s) and letter of authority and only monitor data from subjects with a correct signature on these forms. The monitor shall also be responsible for notifying such deficiencies in writing to the investigator and convene with the clinical investigation site personnel appropriate and timely corrective actions.

The first monitoring visit at the site should be conducted as soon as reasonably possible after the first subject(s) has(have) completed the first visit of the investigation. This is to minimise systematic errors done by site and to clarify potential questions before proceeding with enrolment of more subjects.

Additional monitoring will be conducted in accordance with the recruitment rate or if there is a need for more frequent visits upon request from site or Clinical Manager.

Written informed consent, in- and exclusion criteria and all AEs occurring in the investigation will be 100% verified for timely completion for all subjects enrolled in the investigation. Investigation Site File shall be monitored for 100% completion per the Investigation File Requirement Checklist. Monitoring activities will be documented in a site visit report. A follow up summary describing the observation(s) and actions required shall be provided as soon as reasonably possible to the investigator after the conducted monitoring visit.

The sponsor representative (Clinical Manager) will have close contact to the site in the recruitment period to ensure that any concerns, problems or recruitment challenges are solved with the site in a timely manner.

Close-out visit will be performed when all subject visits have been finalised, queries have been solved and database locked.

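### After termination the plan asks completers only for serious adverse events, so late non-serious device effects are not solicited, and the final status of ongoing events is documented after database lock

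*Combined protocol and SAP*

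**What the plan says.** Section 17.5 (Medical care of subjects) sets three contact rules. While a subject is in the investigation, she is to tell the investigator about any AE. In the week after termination the rule is narrower: "the investigator will inform the subjects to contact him should SAEs occur within one week of the subject is terminated from the investigation". After that week it widens again, but to a different recipient: "Subjects are informed to contact their general physician in case of any AEs happening later than one week of investigation termination".

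Section 17.4.2 states "There are no anticipated SADEs". Section 17.2 says "Table 2 lists anticipated adverse device effects that may occur"; the five entries are UTI, macroscopic haematuria, macroscopic leukocytes, stinging and pain during catheterisation, and mucosal irritation.

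Section 6.3 has its own first-week rule for subjects who stop early: "the subject will be informed to contact the site within the first week after termination in case of questions or issues".

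On follow-up, 17.5 says "All serious adverse events will be followed until a resolution is addressed" and gives no equivalent for non-serious events. It then says "The status of all ongoing adverse events is documented during site close-out". Section 9.3 fixes when that is: "Close-out visit will be performed when all subject visits have been finalised, queries have been solved and database locked".

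**The concern.** Safety is a secondary objective, and the number of AEs is a secondary endpoint (3.1, 5.3). Section 2 gives UTI as the clinical reason for developing better catheters. UTI is also the Table 2 effect most able to appear some days after the last use. Yet the only events requested after termination are serious ones, while the device effects that the plan anticipates are all of the ordinary kind. For a completer, 17.5 gives no reporting instruction for a non-serious event in days 1 to 7.

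Sections 5.6 and 7.6.2 mention home use, and the synopsis has products returned at the termination visit. The last exposure may therefore fall close to termination, with little or no solicited follow-up after it.

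The second issue is one of order. If the status of open events is documented at close-out, and close-out follows lock, the final status is scheduled for a point where it can no longer enter the locked data.

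**Working it through.** The plan states no figure on this point to reproduce. The check sets the passages side by side and then illustrates the scale.

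**1. What is solicited, and when**

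| Period | Completer | Early leaver |
|---|---|---|
| During the investigation, including the termination visit (7.4, 7.8, 17.5) | any AE | any AE |
| Days 1-7 after termination | SAEs only (17.5) | SAEs (17.5), plus any question or issue (6.3) |
| After day 7 | AEs go to the general physician (17.5) | the same; questions go to her own practitioner (6.3) |

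The gap is the middle row for completers: 7 days for each of the 15 planned.

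**2. Follow-up after earlier and final uses.** Tests are 4-14 days apart (5.1), and any AE is solicited throughout. Use at Visits 1 and 2 is thus followed by at least 4 days of full collection. Follow-up after the final use depends on home use, whose description is redacted:
- If home use runs up to termination (assumption), solicited non-serious follow-up after the last use is about 0 days.
- If the last use is at Visit 3 (assumption), it is at least 5 days. The last window in the 7.8 flow-chart is 5-21 days, and the upper limits 21 + 14 + 14 + 21 = 70 agree with the 70 days in 5.9.

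**3. Which Table 2 effects can be lost**
- Stinging and pain are defined as occurring during catheterisation, so they cannot begin after the last use.
- Haematuria and leukocytes are checked by dipstick at the termination visit (7.4, 7.8). The 1-3 days in section 8 is a healing time, not a time to onset, so trauma from recent use would tend still to be visible at that visit.
- UTI and, less clearly, irritation remain.

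**4. Scale, under assumed rates.** The documents give none. Let p be the risk per subject of a device effect and f the share starting after termination.
- Expected subjects with a missed event = 15 × p × f.
- Chance that the trial records at least one = 1 − (1 − p(1 − f))^15.

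| p | Missed, f = 0.10 | Missed, f = 0.25 | Missed, f = 0.50 | Chance of at least one, f = 0 | Chance, f = 0.25 |
|---|---|---|---|---|---|
| 0.05 | 0.075 | 0.188 | 0.375 | 0.537 | 0.436 |
| 0.10 | 0.150 | 0.375 | 0.750 | 0.794 | 0.689 |
| 0.20 | 0.300 | 0.750 | 1.500 | 0.965 | 0.913 |

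The product pf runs from 0.05 × 0.10 = 0.5% to 0.20 × 0.50 = 10% per subject. Table 2 rates UTI as very unlikely, which points to the low end. One missed subject would be 1/15 = 6.7% of the sample.

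**5. Order of the status check.** The last AE registration is at the termination visit. A formal data review precedes lock (10.3, 11.1.2). Then come lock, close-out (9.3) and documentation of ongoing-event status (17.5). An AE includes abnormal laboratory findings (17.1), so a dipstick finding first seen at termination can be an AE with no later study visit. The only scheduled record of its outcome then falls after lock. The event itself is registered at termination and enters the count.

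**The case against.** Several points on the other side stand.

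- **Unresolved events are not lost.** A reader might infer that AEs still open at termination miss the data. They do not. They are registered at the visits, all AEs are verified (9.3), and the analysis is a descriptive count (10.5) that final status does not alter. Nor does 17.5 say that status is recorded only at close-out; an interim status could be entered earlier.
- **Late events are not barred.** Under 17.6.1 any adverse device effect that the site becomes aware of goes to the sponsor within 10 days, and 17.5 requires care during and after participation. This limits the gap but does not close it, because completers are not asked to make the site aware.
- **An SAE window is not illogical because none is anticipated.** Such a window exists to catch the unanticipated (17.4.3). The point is what it omits.
- **Sections 6.3 and 17.5 do not flatly contradict each other.** One covers questions and issues from early leavers, the other event reporting. They do give early leavers a wider route than completers.
- **Attribution is weak.** Subjects average at least 2 catheters a day (inclusion criterion 4), so at least 2 × 7 = 14 catheterisations would be expected in that week. These are presumably with other products, since study devices have been returned. A UTI then could not be cleanly assigned. This argues for recording such events separately with the last catheter used, not for leaving them unasked.
- **The scope of follow-up is a design choice** in an exploratory study of 15 subjects without pass/fail criteria. That lowers the weight of the point. But the plan already collects any AE for 4-14 days after the earlier tests, so its own practice supports asking after the last use too.

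**Conclusion.** The point holds as a modest gap in safety ascertainment. For completers, a non-serious device effect that begins after the termination visit is not solicited; UTI is the main candidate. The gap is 7 days per subject. Under the assumed rates it corresponds to between 0.075 and 1.5 subjects with a missed event, probably nearer the bottom. The true size depends on the redacted timing of home use.

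Separately, 17.5 and 9.3 together schedule the status of ongoing AEs after database lock. The AE count is unaffected; only the final status of events still open can miss the locked data.

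A reader might go further and conclude that the plan makes the new catheters look safer than they are. The documents do not support that. Which product is used at home, and for how long, is redacted, so neither the direction nor the size of any effect on the comparison between catheters can be stated.

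**What to change.** 1. Reconcile 17.5 with 6.3 so that the existing one-week contact after termination covers any AE, for completers and early leavers alike. Record the onset date and the last catheter used, and list these events separately from on-study AEs.
2. Enter the latest status of every ongoing AE in the eCRF before the data review meeting that already precedes lock. Keep close-out as a check that nothing has changed.

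Neither change needs a new visit. The cost is a few extra AEs to process, some arising under the subject's other catheters and so hard to attribute, and a database lock no earlier than one week after the last termination visit.

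### Both end levels of the causality scale in section 17.6.1 rest on timing alone, so levels overlap and no rule says which prevails

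*Combined protocol and SAP*

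**What the plan says.** Section 17.6.1 tells the investigator to assess all adverse events, serious or not. It then introduces a five-level scale in a sentence about reporting the SAE. The levels are:

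- The lowest, *Not related*, applies when "the event has no temporal relationship with the use of the test material or the procedures".
- The second, *Unlikely related*, applies when "the relationship with the use of the test material seems not relevant and/or the event can be reasonably explained by another cause".
- The third, *Possibly related*, applies when "the relationship with the use of the test material is weak but cannot be ruled out completely". A default is added: "Cases where relatedness cannot be assessed or no information has been obtained should also be classified as possible".
- The fourth, *Probably related*, applies when "the relationship with the use of the test material seems relevant and/or the event cannot reasonably be explained by another cause".
- The highest, *Definitely related/Causal relationship*, applies when "the event has a temporal relationship with the test material use/application or procedures".

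Section 17.2 uses other words. An adverse event related to use of the investigational device counts as an adverse device effect; such an event "should be marked as related or possibly related on the adverse event form". Sections 17.4.1 and 17.4.3 build the SADE and USADE definitions on the adverse device effect, and section 17.4.2 anticipates no SADEs.

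**The concern.** A causality scale should ask for more evidence as certainty rises. Here the middle levels weigh the strength of the link and other causes, while both ends look only at timing. Two investigators could put the same coincident event at opposite ends of the scale, each following the text.

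Timing separates events poorly in this design. Under section 7.4 each test visit has a nurse catheterisation and a self-catheterisation, so a completer has 3 × 2 = 6 of them, with visits 4-14 days apart. Sections 5.6 and 7.6.2 also mention home use. Subjects enter as users of at least 2 catheters a day on average, so if their usual catheterisation continues between visits, a competing cause will often be present. Headache and dizziness, the examples of adverse events in section 17.1, are events for which timing alone says little.

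At stake is which serious events are called device effects. Safety is a secondary objective, and section 20 reserves use of the data for regulatory purposes.

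**Working it through.** The plan states no figure on this point and no arithmetic applies. The check is a literal reading of the five definitions, followed by a trace of where the result is used.

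**Step 1: what each level asks for**

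| Level | Timing | Strength or relevance of link | Other cause |
|---|---|---|---|
| Not related | none present | not mentioned | not mentioned |
| Unlikely | not mentioned | not relevant, and/or → | reasonably explains the event |
| Possibly | not mentioned | weak, not excluded | also possible |
| Probably | not mentioned | relevant, and/or → | does not reasonably explain the event |
| Definitely/Causal | present | not mentioned | not mentioned |

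The two end rows are complements: an event either has a temporal relationship or it does not. The end rows also count timing relative to the procedures, whereas the middle rows refer only to the test material. The term *temporal relationship* is not defined.

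**Step 2: which levels fit an event that is temporally related to use**

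- With a clear other cause: *Definitely* and *Unlikely* both fit; *Not related* is ruled out.
- With a weak link that cannot be excluded: *Definitely* and *Possibly* both fit.
- With no other reasonable cause: *Definitely* and *Probably* both fit.
- Where relatedness cannot be assessed: the default gives *Possibly*, although the timing criterion of *Definitely* is met.

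The and/or wording adds a smaller overlap: an event whose link seems relevant but which another cause could reasonably explain satisfies one arm of *Probably* and one arm of *Unlikely*. Section 17.6.1 has no precedence rule for any of these cases.

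**Step 3: where the level is used**

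- SAE reports to the sponsor (section 17.6.1): within 24 hours, whatever the relatedness. Not affected.
- SAE reports to the authority (section 17.7): all serious adverse events. Not affected.
- Adverse event endpoint (section 10.5): a descriptive count. Not affected.
- SADE and USADE labels (sections 17.4.1 and 17.4.3): depend on the event being a device effect. Exposed.
- Identification of adverse device effects (section 17.2), which have a 10-day report to the sponsor: the two-term marking does not map onto five levels, and *Probably* and *Unlikely* are left unplaced. Exposed only if the scale is meant to govern it, which the plan does not say.

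**The case against.** The strongest defence is that the text forces nothing. The top level is labelled as a causal relationship, which signals more than timing. The middle levels keep their own criteria, and unassessable cases are sent to *Possibly*. The scale is introduced for SAEs, whose reporting does not depend on it. Relatedness enters no stated analysis, section 10.7 applies no pass/fail criteria, and section 7.3 requires the sponsor to train site staff in reporting adverse events.

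Much of this stands. A reader might infer that every event after a catheterisation is sent to the top level and that device effects are therefore misclassified. The documents do not support that: the top level is available to any temporally related event, but a middle level may fit as well. Nor do the two *Likely* rows of Table 2 in section 17.2 show misclassification, since the plan already lists them as anticipated device effects.

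What the defence does not remove is the wording. A label does not replace a criterion, and training cannot supply a precedence rule that the plan lacks. The SAE scope helps only in part. If the scale is for SAEs alone, the unredacted text gives no causality criteria for non-serious adverse device effects.

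**Conclusion.** The scale is wrong as written. Its highest level of certainty needs less evidence than the level below it, a coincident event with a clear other cause cannot be called *Not related*, and overlaps are left unresolved. This is a drafting fault, which should be corrected. Misclassification is a risk that follows from it, not a demonstrated result.

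The consequence is confined to SADE/USADE labels, the identification of adverse device effects where the scale is used for it, and any relatedness statement in the report. With no SADEs anticipated, even one such label would stand out.

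It is tempting to express the size as a shift in a related-event rate among 15 subjects. The plan offers no basis for that. No such rate is planned, 15 is a target for completers with replacements allowed and 2-3 drop-outs expected, and the safety population is everyone with valid consent. The conclusion rests on a literal reading of section 17.6.1 and on the assumption that the adverse event form, which is not in the documents, adds no further criteria.

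**What to change.** In section 17.6.1:

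1. Define *Definitely related* as a temporal relationship **and** no other reasonable explanation, so that it is stricter than *Probably related*.
2. Let *Not related* also cover events with a clearly established other cause.
3. Make the five levels mutually exclusive. *Probably* must be narrowed too, because it already admits an event with no other reasonable cause. Its closing words ("the event cannot reasonably be explained by another cause, but additional information may be obtained") suggest a dividing line: *Probably* while information is outstanding, *Definitely* once other explanations have been excluded. The same line can separate *Unlikely* from *Not related*. Replace the and/or wording, say what counts as a temporal relationship, and refer to test material and procedures in the same way throughout.

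In section 17.2, state which of the five levels count as an adverse device effect, and whether the scale applies to non-serious adverse events.

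The cost is a few lines in two sections and matching form text, submitted as an amendment under section 15.1. No new data, visits or analyses are needed. Serious events already assessed would have to be read again against the new wording.
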